Table 8: Summary of Analyses Related to the Key Confirmatory Secondary Endpoint of Change from Baseline in Modified vdH-S Score at Week 24	41
Table 9: DAS28 (CRP) Response Criteria.....	47
Table 10: Summary of Estimands, Analysis Sets, Data Handling Rules, and Analysis Methods for Endpoints of Signs & Symptoms and Physical Function.....	53
Table 11: Summary of Estimands, Analysis Sets, Data Handling Rules, and Analysis Methods for Endpoints of Skin Disease.....	62
Table 12: Summary of Estimands, Analysis Sets, Data Handling Rules, and Analysis Methods for Endpoints of Nail Psoriasis	67
Table 13: Summary of Estimands, Analysis Sets, Data Handling Rules, and Analysis Methods for Endpoints of HRQOL	70
Table 14: Summary of Estimands, Analysis Sets, Data Handling Rules, and Analysis Methods for Endpoints of Joint Structural Damage	75
Table 15: Markedly Abnormal Vital Signs.....	85
Table 16: Demographic Variables.....	95
Table 17: Summary of Multiple Imputation Method	113

Figures

Figure 1: Schematic Overview of the Study Through End of Study.....	12
Figure 2: Multiplicity Control.....	26

VERSION HISTORY

Table 1: SAP Version History Summary

SAP Version	Approval Date	Change	Rationale
1	2021-10-01	Not Applicable	Initial release
2	2022-09-08	
 Replaced COVID-19 related wording for ICEs and missing data handling to refer only to site closure, site access restrictions, or lockdowns caused by COVID-19 (Natural Disaster). FAS analysis set changed to equal all randomized participants Analysis window for radiographic assessments changed from +/-8 weeks, into Study Week - 6 to Study Day 1 for bl, +/-2 for Week 24; sensitivity analysis added for subgroup with narrower baseline window of Study Week -4 to Study Day 1; a sensitivity analysis added using 2-Step MI to utilize out-of-window data; a sensitivity analysis added using original window of +/- 8 weeks. Added tipping point sensitivity analysis for Primary Endpoint based on Adjusted Composite Estimand with MI for missing data; removed the similar tipping point supplementary analysis using the Treatment Policy Estimand Clarified use of re-reads for Xray is solely to assess the intra-reader and inter-reader variability and calculate the intra-class correlation Added thromboembolic AE events for safety 	Received regulatory agency feedback for guselkumab programs

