5.1.1.2. Visit Windows for Radiographic Assessments and Analyses

The windows for taking radiographs of hands and feet at respective scheduled visits are specified as follows:

All eligible participants should have radiographs taken approximately 2 weeks but not greater than 4 weeks prior to randomization.

Week 24 radiographs should be taken within \pm 2 weeks of the Week 24 visit. For participants who discontinue study intervention prior to Week 24, radiographs of the hands and feet should be performed at the Week 24 visit.

Week 48, 96, and 156 radiographs should be taken within \pm 2 weeks of the Week 48, 96 and 156 visits. For participants who permanently discontinue study intervention after Week 24 but prior to Week 156, and participation at any time during the study radiographs of hands and feet should be performed at the time of discontinuation of study intervention or as soon as possible unless another set of radiographs has been obtained within the past 6 weeks.

The analytical window (inclusive) to be used in radiographic data analyses will be as follows:

- Screening (baseline) analysis visit: Study week -6 to study day 1
- Week 24 analysis visit: \pm 2 weeks around study week 24
- Weeks 48, 96, and 156 analysis visit: \pm 8 weeks around their respective study weeks

Radiographs taken at end of study intervention will be slotted based the analysis window to the appropriate visits to be included in the data analysis.

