5.3.5.2. Sensitivity and Supplementary Analyses

1. **(Sensitivity Analysis 1)** To evaluate the robustness of the **Adjusted Treatment Policy Estimand** regarding the assumptions for missing data, two-dimensional tipping point analyses based on FCS MI imputed data will be performed to evaluate the deviation from the assumption of MAR for missing data (Section 5.3.2.1) using the same MI imputed dataset as that used for the main analysis. Note that data imputed as part of the ICE strategy (MI due to meeting ICEs 4 and 5) will be performed prior to the tipping point analysis. The same analyses method as that for the main analysis, will be fitted for each combination of deltas. The analysis results from the N imputation datasets will be combined, according to Rubin (Rubin 1987) and the p-value for testing the treatment difference will be obtained.

2. **(Sensitivity Analysis 2)** To assess the effect of including all randomized participants, even those from sites rendered unable to support key study operations due to Natural Disaster or Major Disruption, the same analysis as the main analysis will be performed on the FAS analysis set.
3. **(Sensitivity Analysis 3)** To assess the influence of outliers and extreme observations, a trimmed analysis will be performed. The same analysis method as for the main analysis, ANCOVA on multiply imputed data, will be performed on a subset of data where k% (k ranging from 1 to 10) of data are removed from the highest and lowest change scores of modified vdH-S in each intervention group.
4. **(Sensitivity Analysis 4)** To assess the influence of difficult to read radiographs. The same analysis method as for the main analysis, ANCOVA on multiply imputed data, will be performed on a subset of data where participants randomized to the HRV randomization strata are excluded.
5. **(Sensitivity Analysis 5)** An analysis similar to the main analysis, except replacing the randomization stratification factor in the ANCOVA analysis model with the baseline covariates: number of joints with erosion (numeric), log-transformed CRP (mg/dL, numeric), and oral corticosteroid use (Y/N).
6. **(Sensitivity Analysis 6)** To assess the impact of a narrower baseline window, the same analysis as the main analysis will be performed, but only participants with baseline and Week 24 observations within +/- 2 weeks of the expected assessment time, ie, study week -2 for baseline and study week 24 for Week 24 respectively, are included in the analysis.

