7. **(Sensitivity Analysis 7)** To assess the impact of using the original analysis window, the same analysis as the main analysis will be performed, but both baseline and Week 24 observations within +/- 8 weeks of the expected assessment time, ie, study week -2 for baseline and study week 24 for Week 24 respectively, are included in the analysis.
8. **(Sensitivity Analysis 8)** To use all collected post-bl data even outside of the 2 week analysis window, a 2-step MI will be used for imputation: 1) Missing Week 24 data from participants with an x-ray measurement at baseline and a measurement post-baseline during the placebo controlled period will be imputed through a mixed effect linear growth curve (MLGC) model (see Section 6.13); 2) Other missing data will be imputed using the FCS regression method based on the imputed dataset from the 1st step. The 2-step MI will be applied only to the modified vdH-S score and not the erosion or JSON scores.
9. **(Sensitivity Analysis 9)** To assess the effect of excluding all Ukrainian participants from the analysis, as all sites in Ukraine have been impacted by Major Disruption (e.g., study intervention interruptions, temporary site closures, etc) to a larger or smaller extent. The same analysis as the main analysis will be performed on the mFAS-UKR analysis set.
10. **(Sensitivity Analysis 10)** As the Major Disruption has the potential to prevent SDV from taking place (e.g, due to site closure, site inaccessibility, etc), an analysis will be conducted to assess the impact by excluding affected participants. The same analysis as the main analysis will be performed on the mFAS analysis set, excluding participants for which expected SDV was not completed for data on or prior to Week 24.
11. **(Supplementary Analysis 1)** To support regulatory decision making, an analysis based on the **Treatment Policy Estimand** will be performed. The observed modified vdH-S score for participants will be used regardless of whether or not ICE criteria are met prior to Week 24,

and missing modified vdH-S score will be imputed using FCS MI under the assumption that data are MAR. The same analysis method as the main analysis will be performed. The analysis will be performed based on the mFAS-UKR analysis set.

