Sensitivity Analysis 3/ mFAS/ Adjusted Treatment Policy	ICEs 4 and 5, data not used, but rather imputed using FCS MI Missing data assumed MAR, imputed via FCS MI	
 Trimmed analysis: k% (k ranging from 1 to 10) of data are removed from the highest and lowest change scores of in each intervention group. Summarized descriptively at each level of k Treatment comparisons including p-value from combining ANCOVA model treatment difference across multiply imputed datasets, separately at each level of k

Table 8: Summary of Analyses Related to the Key Confirmatory Secondary Endpoint of Change from Baseline in Modified vdH-S Score at Week 24

Analysis/Population/Estimand	ICE/Missing data imputation	Additional notes
Sensitivity Analysis 4/ mFAS excluding HRV participants/ Adjusted Treatment Policy	ICEs 4 and 5, data not used, but rather imputed using FCS MI Missing data assumed MAR, imputed via FCS MI	
 Analysis for non-HRV participants Summarized descriptively Treatment comparisons including p-value from combining ANCOVA model treatment difference across multiply imputed datasets
Sensitivity Analysis 5/ mFAS/ Adjusted Treatment Policy	ICEs 4 and 5, data not used, but rather imputed using FCS MI Missing data assumed MAR, imputed via FCS MI	
 Summarized descriptively Treatment comparisons including p-value from combining ANCOVA model treatment difference across multiply imputed datasets.
Sensitivity Analysis 6/ mFAS excluding participants with baseline assessment outside +/- 2 weeks of Week -2/ Adjusted Treatment Policy	ICEs 4 and 5, data not used, but rather imputed using FCS MI	
 Summarized descriptively Treatment comparisons including p-value from combining ANCOVA model treatment difference across multiply imputed datasets
Sensitivity Analysis 7/ mFAS/ Adjusted Treatment Policy	ICEs 4 and 5, data not used, but rather imputed using FCS MI	
 Analysis window using +/- 8 weeks for both bl and Week 24 Summarized descriptively Treatment comparisons including p-value from combining ANCOVA model treatment difference across multiply imputed datasets

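### For the modified vdH-S endpoint, the text of Sensitivity Analysis 6 adds a Week 24 film requirement that contradicts its purpose and Table 8, so it changes the missing-data handling along with the baseline window

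*SAP*

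**What the plan says.** All of this concerns the key confirmatory secondary endpoint, change in modified vdH-S score at Week 24.

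- **Main analysis windows (SAP 5.1.1.2).** The baseline window is "Screening (baseline) analysis visit: Study week -6 to study day 1". The Week 24 window is ± "2 weeks around study week 24".
- **Main analysis missing data (SAP 5.3.5.1.3).** Data missing for any reason are imputed by FCS multiple imputation.
- **Sensitivity Analysis 6, text (SAP 5.3.5.2).** The purpose is given as: "To assess the impact of a narrower baseline window, the same analysis as the main analysis will be performed". The inclusion rule is then "only participants with baseline and Week 24 observations within +/- 2 weeks of the expected assessment time", centred on study week -2 and study week 24.
- **Sensitivity Analysis 6, Table 8.** The population is "mFAS excluding participants with baseline assessment outside +/- 2 weeks of Week -2". There is no Week 24 condition. The data-handling cell mentions imputation for intercurrent events 4 and 5 but has no line on other missing data.
- **Sensitivity Analysis 7, text (SAP 5.3.5.2).** It restores the original window and uses "both baseline and Week 24 observations within +/- 8 weeks of the expected assessment time, ie, study week -2 for baseline"; the later film is centred on study week 24.
- **Background only.** The SAP version history describes the version 2 addition as a "sensitivity analysis added for subgroup with narrower baseline window of Study Week -4 to Study Day 1".

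**The concern.** A sensitivity analysis is informative when it varies one feature and holds the rest fixed. Analysis 6 is meant to vary the baseline film window. Its text also requires an observed, in-window Week 24 film, and having one is a post-randomization event. Participants whose Week 24 score the main analysis imputes are left out. Agreement or disagreement with the main result would then reflect two changes at once, and nothing in the output would separate them.

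The conflict with Table 8 matters in practice: one programmer following the text and another following the table would build different datasets.

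Analysis 7 raises a smaller question. Its window has no stated limit at the first dose or at the Week 24 crossover, and the SAP does not say how a placebo-group film taken after active treatment has begun is to be treated.

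**Working it through.** **1. Windows, from the stated centres and half-widths**

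| Analysis | Baseline film | Week 24 film |
|---|---|---|
| Main | Week -6 to Day 1 | 24 ± 2 = Week 22 to 26 |
| Sensitivity 6, text | -2 ± 2 = Week -4 to 0 | 24 ± 2 = Week 22 to 26 (required) |
| Sensitivity 6, Table 8 | -2 ± 2 = Week -4 to 0 | no condition |
| Sensitivity 7 | -2 ± 8 = Week -10 to +6 | 24 ± 8 = Week 16 to 32 |

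At Week 24 the text of Analysis 6 and the main analysis use the same window. The condition can only remove participants without an in-window film.

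**2. Participants removed under the text of Analysis 6**

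The missing-film rate is not in the documents, so I assume 3% to 20%. Applying it to 350/250/350 and rounding within arm:

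| Missing | N left of 950 | Dropped |
|---|---|---|
| 3% | 922 | 28 |
| 5% | 902 | 48 |
| 10% | 855 | 95 |
| 15% | 808 | 142 |
| 20% | 760 | 190 |

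Under Table 8 nobody is dropped for a missing Week 24 film.

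**3. Power at those sizes**

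The plan's own figures come first. SAP Tables 4 and 5, base rows: 15% zeros, otherwise normal with SD 3.4 and means 1.33 (placebo), 0.29 (q4w) and 0.53 (q8w). The test is ANOVA on van der Waerden scores, two-sided 0.05, with 10,000 runs. I obtain 92.3% for q4w (stated 92%) and 81.0% for q8w (stated 80%).

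With 3% to 20% removed (4,000 runs per row), power is about 91% to 86% for q4w and 80% to 72% for q8w. These falls are relative to complete data. Imputed scores add little information, so the loss relative to the main analysis would be smaller. Power is therefore not the main issue.

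**4. How far the missing-data change alone could move an arm mean**

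Let m be the fraction missing in an arm, and d the amount by which the imputed scores differ on average from that arm's observed scores. Dropping instead of imputing shifts the arm mean by m × d. With m = 0.05, 0.10 and 0.15:

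- d = 0.5 gives 0.025, 0.05 and 0.075
- d = 1 gives 0.05, 0.10 and 0.15
- d = 2 gives 0.10, 0.20 and 0.30

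The design differences are 0.25 - 1.13 = -0.88 (q4w) and 0.45 - 1.13 = -0.68 (q8w). The values of d are illustrative. A shift arises in the contrast only as far as m × d differs between arms. Such a difference is possible because the imputation model conditions on the seven ACR components over time (SAP Appendix 11), which a complete-film ANCOVA does not use.

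**5. Direction of any effect in Analysis 7**

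Assume linear progression at (Week 24 mean)/24 per week, with the crossed-over placebo group moving at once to the q4w rate.

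- Week 16: q4w -0.88 × 16/24 = -0.59; q8w -0.68 × 16/24 = -0.45
- Week 32, placebo: 1.13 + (0.25/24) × 8 = 1.213
- Week 32, q4w: (0.25/24) × 32 - 1.213 = 0.333 - 1.213 = -0.88
- Week 32, q8w: (0.45/24) × 32 - 1.213 = 0.600 - 1.213 = -0.61
- Week 32 with no crossover effect: q4w -0.88 × 32/24 = -1.17; q8w -0.68 × 32/24 = -0.91

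**The case against.** **Table 8 already has the right rule, and the stakes are low.** Analysis 6 is one of ten sensitivity analyses, outside the fixed-sequence test, and departures from MAR are examined separately by tipping point. This stands, and it limits the point to a repair of wording. But Table 8 does not settle the conflict. The rows for Analyses 2 to 5, 9 and 10 state that missing data are imputed under MAR; the rows for 6 and 7 do not. The text remains a competing definition.

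**Stronger readings that the documents do not support:**

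- *Neither analysis tests the film window.* Analysis 6 as defined in Table 8 does test the baseline window, and Analysis 7 tests the original window, which is its stated purpose. Analysis 8 adds out-of-window films limited to the placebo-controlled period.
- *Analysis 6 is a completer analysis.* Even under the text, participants who stopped treatment but have an in-window Week 24 film stay in. So do those with intercurrent event 4 or 5 and such a film, whose values are imputed.
- *Analysis 7 will use on-drug baseline films.* Inclusion criterion 5 and the randomization strata need a central read before randomization, and films are due no more than 4 weeks before it. The protocol plans no film between screening and Week 24 except at study discontinuation. The gap is a missing formal limit.
- *Analysis 7 pulls the contrast toward the null.* In the working, late films leave q4w at -0.88 and move q8w only from -0.68 to -0.61. Early films dilute more. Appendix 12 also sends early-discontinuation films after Week 26 to the next read campaign, while Week 24 comparisons use Read Campaign 1. What remains is late films from participants still on study, whose number is unknown.
- *Film intervals would run from 10 weeks (6 to 16) to 42 weeks (-10 to 32).* These are the arithmetic limits of the windows. No schedule produces a baseline film at Week 6. Week -10 lies outside the 4-week rule and outside a 6-week screening period extendable by 2 weeks.

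**Conclusion.** The point holds for Sensitivity Analysis 6. Its text conflicts with its stated purpose and with Table 8. Read literally, it changes the baseline window and the handling of missing Week 24 films together and selects on a post-randomization event, so it cannot answer the question it poses. Under assumed missing rates of 3% to 20%, 28 to 190 of 950 participants would be dropped for a reason unrelated to the baseline film. The true rate is not in the documents.

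For Sensitivity Analysis 7 the finding is narrower: no stated limit at first dose, and no account of placebo-group films taken after active treatment starts. The size and direction of any effect are not established.

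Neither analysis enters the confirmatory test. Type I error and the main estimate are unaffected.

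**What to change.** **Sensitivity Analysis 6**

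- In Section 5.3.5.2, delete the reference to Week 24 observations in the inclusion rule, together with the matching clause that gives study week 24 as their expected time.
- Restrict on baseline film timing only (Study Week -4 to Study Day 1), as Table 8 does.
- In the Table 8 row, add that missing Week 24 data are assumed MAR and imputed via FCS MI, as in the main analysis. The row for Analysis 7 lacks the same line and can be completed at the same time.

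**Sensitivity Analysis 7**

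- Keep the 8-week window on both sides. Reproducing the original window is its purpose, and capping only the late side would keep the early films that dilute more.
- State that a baseline film must predate the first dose.
- Report how many placebo-group films were taken after the first active dose, and repeat the analysis excluding those films.

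The cost is SAP wording and one additional run of Analysis 7. Data collection, sample size and the testing sequence do not change.

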5.3.5.3. Subgroup Analyses

Subgroup analyses will be performed using the Adjusted Treatment Policy Estimand using the same ANCOVA model on the multiply imputed data as the main analysis to evaluate treatment consistency over baseline demographics, baseline disease characteristics, baseline modified vdH-S score, and prior and baseline medication use. A forest plot will be produced for all subgroups listed in Section 5.5.6. The LSMean for each intervention group, LSMean difference between intervention groups, and the corresponding 95% CIs will also be provided for each of subgroups (Section 5.3.1). In addition, the p-values for interaction of the intervention groups and the subgroups will also be provided when a subgroup has at least 2 categories, and will be calculated based on the **observed data**.

If the number of participants in a subgroup is too small (eg., < 10), subgroups may be pooled for analyses.

5.3.5.4. Exploratory Analyses

An exploratory analysis may be conducted for the change from baseline to Week 24 in modified vdH-S, similar to the main analysis, except that data observed after missing any active (ie, guselkumab) dose will not be used and instead imputed using FCS MI assuming MAR. Additional analyses of radiographic data will be explored using computer vision based AI models.

5.3.5.5. Summary of Analyses Related to the Key Confirmatory Secondary Endpoint of Change from Baseline to Week 24 in Modified vdH-S Score

Table 8 below provides an overview on all the analyses related to the key confirmatory secondary endpoint of change from baseline to Week 24 in modified vdH-S score, the data handling rules to be used, and the analysis methods and summary statistics. For subgroup analyses the analysis sets are further subset to the individual subgroups. Section 5.3.2 provides a summary of the Multiple Imputation method.

Table 8: Summary of Analyses Related to the Key Confirmatory Secondary Endpoint of Change from Baseline in Modified vdH-S Score at Week 24

Analysis/Population/Estimand	ICE/Missing data imputation	Additional notes
Main Analysis/ mFAS/ Adjusted Treatment Policy	ICEs 4 and 5, data not used, but rather imputed using FCS MI Missing data assumed MAR, imputed via FCS MI	
 Summarized descriptively Treatment comparisons including p-value from combining ANCOVA model treatment difference across multiply imputed datasets
Sensitivity Analysis 1/ mFAS/ Adjusted Treatment Policy	ICEs 4 and 5, data not used, but rather imputed using FCS MI Missing data imputed using FCS MI, then imputed data varied	
 2-dimensional tipping point analysis to assess robustness of analysis results should there be deviation from MAR assumption of missing data; graphical P-value from combining ANCOVA model treatment difference across multiply imputed datasets, for each coordinate on the graph separately.
Sensitivity Analysis 2/ FAS/ Adjusted Treatment Policy	ICEs 4 and 5, data not used, but rather imputed using FCS MI Missing data assumed MAR, imputed via FCS MI	
 Summarized descriptively Treatment comparisons including p-value from combining ANCOVA model treatment difference across multiply imputed datasets
Sensitivity Analysis 3/ mFAS/ Adjusted Treatment Policy	ICEs 4 and 5, data not used, but rather imputed using FCS MI Missing data assumed MAR, imputed via FCS MI	
 Trimmed analysis: k% (k ranging from 1 to 10) of data are removed from the highest and lowest change scores of in each intervention group. Summarized descriptively at each level of k Treatment comparisons including p-value from combining ANCOVA model treatment difference across multiply imputed datasets, separately at each level of k

Table 8: Summary of Analyses Related to the Key Confirmatory Secondary Endpoint of Change from Baseline in Modified vdH-S Score at Week 24

Analysis/Population/Estimand	ICE/Missing data imputation	Additional notes
Sensitivity Analysis 4/ mFAS excluding HRV participants/ Adjusted Treatment Policy	ICEs 4 and 5, data not used, but rather imputed using FCS MI Missing data assumed MAR, imputed via FCS MI	
 Analysis for non-HRV participants Summarized descriptively Treatment comparisons including p-value from combining ANCOVA model treatment difference across multiply imputed datasets
Sensitivity Analysis 5/ mFAS/ Adjusted Treatment Policy	ICEs 4 and 5, data not used, but rather imputed using FCS MI Missing data assumed MAR, imputed via FCS MI	
 Summarized descriptively Treatment comparisons including p-value from combining ANCOVA model treatment difference across multiply imputed datasets.
Sensitivity Analysis 6/ mFAS excluding participants with baseline assessment outside +/- 2 weeks of Week -2/ Adjusted Treatment Policy	ICEs 4 and 5, data not used, but rather imputed using FCS MI	
 Summarized descriptively Treatment comparisons including p-value from combining ANCOVA model treatment difference across multiply imputed datasets
Sensitivity Analysis 7/ mFAS/ Adjusted Treatment Policy	ICEs 4 and 5, data not used, but rather imputed using FCS MI	
 Analysis window using +/- 8 weeks for both bl and Week 24 Summarized descriptively Treatment comparisons including p-value from combining ANCOVA model treatment difference across multiply imputed datasets
Sensitivity Analysis 8/ mFAS/ Adjusted Treatment Policy	ICEs 4 and 5, data not used, but rather imputed using MI 2-step MI	
 Summarized descriptively Treatment comparisons including p-value from combining ANCOVA model treatment difference across multiply imputed datasets

Table 8: Summary of Analyses Related to the Key Confirmatory Secondary Endpoint of Change from Baseline in Modified vdH-S Score at Week 24

Analysis/Population/Estimand	ICE/Missing data imputation	Additional notes
Sensitivity Analysis 9/ mFAS-UKR/ Adjusted Treatment Policy	ICEs 4 and 5, data not used, but rather imputed using FCS MI Missing data assumed MAR, imputed via FCS MI	
 Summarized descriptively Treatment comparisons including p-value from combining ANCOVA model treatment difference across multiply imputed datasets
Sensitivity Analysis 10/ mFAS, Excluding Participants with Non-SDV'd Data Through Week 24/ Adjusted Treatment Policy	ICEs 4 and 5, data not used, but rather imputed using FCS MI Missing data assumed MAR, imputed via FCS MI	
 Summarized descriptively Treatment comparisons including p-value from combining ANCOVA model treatment difference across multiply imputed datasets
Supplementary Analysis 1/ mFAS-UKR/ Treatment Policy	ICEs considered irrelevant Missing data assumed MAR, imputed via FCS MI	
 Summarized descriptively Treatment comparisons including p-value from combining ANCOVA model treatment difference across multiply imputed datasets
Supplementary Analysis 2/ mFAS-UKR/ Treatment Policy	ICEs considered irrelevant Missing data imputed using FCS MI, then imputed data varied	
 2-dimensional tipping point analysis to assess robustness of analysis results should there be deviation from MAR assumption of missing data; graphical P-value from combining ANCOVA model treatment difference across multiply imputed datasets, for each coordinate on the graph separately.
Subgroup Analyses/ mFAS into subgroup categories/ Adjusted Treatment Policy	ICEs 4 and 5, data not used, but rather imputed using FCS MI Missing data assumed MAR, imputed via FCS MI	
 LSMean difference and 95% CI from combining ANCOVA model estimates across multiply imputed data P-value from ANCOVA model for the interaction of intervention group and subgroup variable, using

Table 8: Summary of Analyses Related to the Key Confirmatory Secondary Endpoint of Change from Baseline in Modified vdH-S Score at Week 24

Analysis/Population/Estimand	ICE/Missing data imputation	Additional notes
		
observed data and NOT MI imputed data
 
 • Graphical: forest plots

